7.1 Outcome Definitions

7.1.1 Feasibility Outcomes (Primary)

The pre-specified primary outcomes are as follows:

	Outcome	Definition	Target
1	Recruitment rate	Number of participants recruited per month at each site (total eligible randomized patients per site divided by date of last randomized patient at that site minus date of first randomized patient at that site, with month defined as 30.4 days. This will exclude first phase of KGH enrollment), as well as an overall crude average of each site’s rate.	>4.17 per month
2	Compliance with study medication	Proportion of prescribed doses received (divide received doses by prescribed for each patient to get a patient level measure before summarizing).	≥90% of prescribed
3	Dropout rate	Proportion of participants who dropped out from the trial (1-[% of randomized patients who either have a known date of death during the study period OR have a non-missing CAC value measured at least 6 months after randomization]).	<20%
4	Adherence to study protocol	Proportion of participants who adhered to the study protocol (90% study medication compliance and not dropped out) (all pooled).	≥80%
5	Rates of eligible patients consented and randomized	Proportion of eligible patients who were A) consented and B) randomized to the study.	No target

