4.1 Trial Design

The current iPACK-HD pilot trial is a prospective randomized parallel two-arm double-blind 3-centre feasibility and exploratory phase II trial in adults with ESKD requiring dialysis who have a baseline CAC score ≥ 30 Agatston units (AUs). Eligible patients were randomly assigned 1:1 to either the experimental treatment group (10 mg of phylloquinone thrice weekly) or to a control group (matching placebo thrice weekly). The initial plan was to roll patients from this pilot feasibility trial into a full definitive phase II RCT. However, due to pragmatic considerations including challenges obtaining Canadian Institutes of Health Research (CIHR) funding, this study is now a stand-alone pilot feasibility and exploratory phase II trial. If the results of this trial suggest that a large scale definitive RCT is warranted, then the feasibility and preliminary results will be used to help support the design and funding application for the definitive trial.

The protocol for the planned definitive RCT is published in the Canadian Journal of Kidney Health and Disease.² The protocol for this pilot feasibility trial is a successful grant application from the March 2015 CIHR RCT committee.

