4.3 Sample Size Considerations

The original protocol sample size is quoted below:

The multicenter pilot study will enroll a total of 50 patients from 3 Canadian Centers and 1 US site. We will combine these data with 30 patients from the single-center iPACK-HD pilot study at Queen's University for a total sample size of 80 patients. Table 1 [in appendix B] describes the probability of meeting feasibility outcome 1 to 4 under a range of true population values. With 80 patients, the overall rate of CAC progression will have at least a 63% and 95% chance of being estimated within $\pm 5\%$ and $\pm 10\%$ of the true population value respectively. Therefore, the total pilot sample size (n=80) should be adequate to reliably assess the feasibility of the fully-powered multi-center study. We believe a total sample size of 30 patients from Queen's University and 50 patients from 3 Canadian sites and 1 US site for a total of 80 patients will be adequate to thoroughly pilot the trial procedures and obtain acceptably accurate estimates for the study outcomes. The pilot study will not be used to determine effect size but will provide further information regarding the distribution of our primary outcome that will allow us to further refine a definitive sample size estimate. We anticipate that, to optimally power the definitive Phase II study, we need approximately 430 patients.

Since the original protocol did not anticipate that we would perform any by-arm comparisons, these are not addressed in the above sample size consideration quoted from the pilot protocol. Without adjustment for covariates or multiplicity of outcomes, a sample size of 40 per arm would achieve 80% power at a two-sided $\alpha=0.05$ to compare means between groups using the two-sample t-test for approximately normal outcomes (regardless of equality of variance) if the population mean difference between arms was 63% of the within group standard deviation. If the Wilcoxon rank-sum test was used, we would achieve 80% power if the concordance index between the treatment arm and outcome value was 0.68. For binary outcomes (such as mortality or fracture), the sample size would achieve at least 80% power as long as the absolute difference in proportions between groups was 30%.

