5.1 Confidence Intervals and P-values

Feasibility outcomes will be provided descriptively as rates or proportions. To meet the feasibility target, the point estimate of the observed feasibility metric simply needs to meet or exceed the target.

Most variables will be described within arm and compared between arms using two-sided p-values stratified by site and diabetes status. We will consider a p-value <0.05 to indicate statistical significance. In this exploratory phase II study, we will not formally adjust p-values for multiplicity of tests, but will consider the potential type I and type II errors in our interpretation of results. False discovery rates may be used to help interpret nominal statistical significance of the unadjusted p-values.

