Below we provide the probability of reaching the study's feasibility targets with 80 participants. We believe that a total of 80 participants are sufficient but not excessive to ensure that it is highly probable that the study's targets will be met if and only if they should be.

1. *Recruitment of trial patients in the multi-centre iPACK-HD pilot study: Successful recruitment in the multi-centre iPACK-HD pilot trial will be defined as enrolling 50 patients in 12 months from the 4 study sites in the multi-centre pilot study (average monthly accrual ≥ 4.17). If the true accrual per month follows a Poisson distribution with a rate of 6 per month, as we expect based on recruitment rates in the iPACK-HD single-centre pilot study at Queen's University, then the chance of meeting the target will be 99.7%. On the other hand, if the true recruitment rate was an unacceptably low at 3 per month, then the chance of meeting the recruitment feasibility target will only be 1.6%.*
2. *Compliance with study medication: Successful adherence will be defined as $\geq 90\%$ of prescribed intervention being administered. For true adherence rates of 80%, 85% and 95% the chance of meeting the target will be 1%, 13% and 98% respectively.*
3. *Dropout rate: Successful rate of loss to trial completion will be defined as $\geq 80\%$ of randomized patients completing the trial. For true completion rates of 70%, 75%, 85% and 90% the probability of meeting the target will be 3%, 18%, 92%, and 99.8% respectively.*

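### The recruitment target of 4.17 per month is an all-sites total, but SAP section 7.1.1 sets it against per-site rates and their unweighted average

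*SAP*

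**What the plan says.** Section 7.1.1, outcome 1, defines the recruitment rate as "Number of participants recruited per month at each site (total eligible randomized patients per site divided by date of last randomized patient" minus the date of the first at that site, with a month taken as 30.4 days and the first phase of KGH enrolment left out. The row continues "as well as an overall crude average of each" site's rate. The target cell asks for more than 4.17 per month and does not say whether that is per site or in total.

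Appendix B, item 1, shows where the figure comes from. Success there is "enrolling 50 patients in 12 months from the 4 study sites in the multi-centre pilot study (average monthly accrual ≥ 4.17"). The appendix then gives the chance of success: "If the true accrual per month follows a Poisson distribution with a rate of 6 per month", "then the chance of meeting the target will be 99.7"%. At a true rate of 3 per month, which it calls unacceptably low, the chance is 1.6%. Section 4.3 agrees that 50 is the combined figure: the multicentre part was to "enroll a total of 50 patients from 3 Canadian Centers and 1 US site".

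Section 5.1 gives the decision rule: "the point estimate of the observed feasibility metric simply needs to meet or exceed the target". Section 4.1 now describes a "double-blind 3-centre feasibility and exploratory phase II trial".

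**The concern.** The threshold and the quantity compared with it are on different scales. Appendix B counts patients over all sites in a fixed 12 months. Section 7.1.1 computes a separate rate for each site, over that site's own first-to-last randomization window, and then averages the site rates without weights. An average over sites does not grow as sites are added, whereas the total does.

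Feasibility is the primary objective, recruitment is the first outcome listed under it, and the verdict rests on a point estimate with no interval. A trial that enrolled 50 patients in 12 months could therefore be reported as having failed its recruitment target. With other site windows, one that recruited too slowly could be reported as having met it. Section 4.1 says the feasibility results are to support the design and funding of the definitive trial, so the label matters.

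**Working it through.** **1. Reproduce the plan's figures.** The inputs are 50 patients, 12 months, and true total rates of 6 and 3 per month (Appendix B, item 1).

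- Target: 50/12 = 4.167 per month.
- At 6 per month, the expected count is 12 × 6 = 72, and P(Poisson(72) ≥ 50) = 0.9974. The plan states 99.7%.
- At 3 per month, the expected count is 12 × 3 = 36, and P(Poisson(36) ≥ 50) = 0.0156. The plan states 1.6%.

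Both match when 6 and 3 per month are accrual summed over sites. That settles the meaning of 4.17.

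**2. Put the same trial through section 7.1.1.** With S sites of equal size recruiting over the same period, the crude average is the total rate divided by S.

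- Goal met exactly: 4.167/3 = 1.39 with 3 sites; 4.167/4 = 1.04 with 4.
- Expected accrual: 6/3 = 2.0; 6/4 = 1.5.
- Total accrual needed for the average to reach 4.17: 3 × 4.17 = 12.5 per month (about 150 patients in 12 months); 4 × 4.17 = 16.7 per month (about 200 patients).

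**3. Allow for the first-to-last denominator.** Under Poisson arrivals, n/(last − first) overstates a site's rate by n/(n − 2) in expectation: 1.25 at n = 10, 1.13 at n = 17 and 1.04 at n = 50. Simulation with this denominator (20,000 runs per setting, equal and unequal site shares, runs with a site of fewer than 2 patients omitted) gave the following for sites recruiting concurrently over 12 months:

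| Accrual | Sites | Median crude average | Chance of exceeding 4.17 |
|---|---|---|---|
| Exactly 50 patients | 3 | 1.56–1.57 | 0 to 0.2% (both rows) |
| Exactly 50 patients | 4 | 1.22–1.25 | |
| Total 6 per month | 3 | 2.17–2.24 | under 0.4% (both rows; Appendix B: 99.7%) |
| Total 6 per month | 4 | 1.68–1.80 | |

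**4. Vary the site windows.** The SAP gives no site start dates, so these windows are assumptions. Each site is active for only part of the 12 months, with staggered starts.

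| Accrual | Sites | 9 months each | 6 months each | 4 months each |
|---|---|---|---|---|
| 72 expected | 3 | <0.1% | about 65% | about 100% |
| 72 expected | 4 | about 0.1% or less | 2–3% | about 95% |
| Exactly 50 | 3 | not run | 0.1% or less | about 100% |
| 36 expected | 3 | not run | not run | 16–18% (Appendix B: 1.6%) |

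With the number of patients held fixed, the verdict moves from almost certain failure to almost certain success as the windows shorten.

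**5. Summing the site rates is not a remedy.** As an illustration, take 20, 15 and 15 patients over 12, 6 and 3 months. The site rates are 1.67, 2.50 and 5.00. Their average is 3.06 and their sum 9.17, while 50 patients over the common 12 months is 4.17.

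**The case against.** The combined criterion is in the SAP: Appendix B states it, and section 4.3 points the reader there for the feasibility outcomes. The target cell in section 7.1.1 carries no per-site label, so an analyst who looked up the origin of 4.17 could apply it to a total. The site windows in step 4 are hypothetical, and the four-site results describe the original plan and not the three-centre trial. The outcome is descriptive, no stated rule makes it a formal go/no-go gate, and a pooled rate can be calculated later from the randomization dates.

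Much of this is fair. The fault is best described as section 7.1.1 contradicting Appendix B: the pooled criterion exists but was not carried into the outcome definition. Attaching 4.17 to the site rates or their average is an inference from the table row, though that row offers nothing else to compare. Neither the pooling over arms in section 4.4 nor the overall descriptive presentation in section 7.2 defines a rate over sites. Section 1.3 says the SAP is there to give analysts clear specifications, and one who follows section 7.1.1 would never compute the quantity that Appendix B sets the target for. The mismatch itself needs no assumption about site windows; only its size does.

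**Conclusion.** The concern holds and should be corrected before the analysis. The figure 4.17 is an all-sites total, and neither quantity defined in section 7.1.1 is.

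If the sites recruited concurrently, the hurdle is about three times the intended one with the current three centres, or four times with the four sites of the original plan. The 99.7% chance of success in Appendix B then becomes less than 0.4%. If the windows were short or staggered, the verdict depends mainly on their length, and success can be declared too easily. Which case applies cannot be told from the SAP.

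The calculations assume Poisson arrivals and the site shares and windows stated. The damage is confined to the met/not-met label for this one primary outcome. No between-arm comparison is touched.

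**What to change.** In section 7.1.1, outcome 1:

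- **Overall rate.** Define it as all eligible patients randomized in the multicentre phase, summed over sites and excluding the first KGH phase, divided by one common calendar recruitment period.
- **Start of the period.** Use first site opening if that date is held. Otherwise run from the first to the last multicentre randomization and state the upward bias (50/48 = 1.04, about 4% at n = 50). This fallback is less exact. With concurrent sites it succeeds 99.7–99.9% of the time at 6 per month and about 3–4% at 3 per month, but 3–17% at 3 per month if starts are staggered, against the planned 1.6%.
- **Comparison.** Use ≥ 50/12, in line with section 5.1 and Appendix B. As written, exactly 50 patients in 12 months gives 4.167 and misses a strict, rounded 4.17.
- **Number of sites.** State that the target was set for four sites and that the trial has three centres.
- **Site rates.** Report them and their crude average descriptively, with no target, and note that the first-to-last denominator overstates rates at small sites.

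The cost is a change of SAP wording and one recalculation. The fallback denominator uses only randomization dates that section 7.1.1 already requires. Section 4.2 indicates that enrolment is complete, so the amendment should be dated and justified by the definition in Appendix B, not by the recruitment achieved.

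### Recruitment rate (7.1.1, outcome 1) counts time only from first to last randomization at each site, which biases every site rate upward and does not match the calendar basis of the 4.17 target

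*SAP*

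**What the plan says.** The first primary feasibility outcome in SAP 7.1.1 is a site-level rate: the count of eligible patients randomized there, "divided by date of last randomized patient at that site minus date of first randomized patient at that site", in months of 30.4 days. The first phase of enrolment at KGH is left out. The table then reports the site rates "as well as an overall crude average of each site’s rate", and sets the target at ">4.17 per month" without saying whether that is per site or in total. No activation or closing date enters the calculation.

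Appendix B, item 1, shows where the target comes from: "enrolling 50 patients in 12 months from the 4 study sites in the multi-centre pilot study". It gives a 99.7% chance of success at a true accrual of 6 per month and 1.6% at 3 per month, which it regards as unacceptable. Section 5.1 judges feasibility on the point estimate alone.

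**The concern.** The numerator counts all n patients at a site, but the denominator covers only the n − 1 gaps between them. Time from activation to the first patient, and from the last patient to the close of enrolment, is lost. Idle months between the first and last patient are kept. If a site has one patient, or randomizes everyone on one day, the denominator is zero, and the SAP has no rule for that case.

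The site rates are reported as a primary outcome, and section 4.1 says that the feasibility results will support the design and funding of a definitive trial. A planner who reads an inflated site rate as accrual per month of open time would ask for too few sites or too short an enrolment period. The pass probabilities in Appendix B also belong to a fixed 12-month count, not to this rate.

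**Working it through.** **1. The plan's own figures.** The target is 50/12 = 4.167 per month. With a Poisson count over 12 months:

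- at 6 per month (mean 72), P(X ≥ 50) = 0.9974;
- at 3 per month (mean 36), P(X ≥ 50) = 0.0156.

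Both match Appendix B, so its probabilities rest on a fixed calendar period with all sites together.

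**2. Bias in one site's rate.** Assume n arrivals spread uniformly over M open months. The expected first-to-last span is M(n − 1)/(n + 1), so the SAP rate is roughly (n + 1)/(n − 1) times the open-time rate n/M.

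| Patients at the site | Approximate ratio |
|---|---|
| 5 | 6/4 = 1.50 |
| 8 | 9/7 = 1.29 |
| 12.5 (50 over 4 sites) | 13.5/11.5 = 1.17 |
| 16.7 (50 over 3 sites) | 17.7/15.7 = 1.13 |
| 20 | 21/19 = 1.11 |

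This is the loss at the two ends under steady accrual. Start-up delay or a final stall adds to it. If 2, 4 or 6 of 12 open months lie outside the first-to-last span, the ratio is 12/10 = 1.20, 12/8 = 1.50 or 12/6 = 2.00.

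**3. Simulation.** Assumptions: equal sites, each open 12 months, Poisson accrual, 20,000 trials per setting, threshold 50/12. The few trials in which a site had fewer than two patients were dropped (at most 84 of 20,000). Section 4.1 gives 3 sites and Appendix B gives 4, so both were run. The ratio column is the sum of the SAP site rates over the open-time total.

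| Sites | True total per month | Median ratio | Median crude average | Crude average passes | Sum of SAP site rates passes | Open-time total passes |
|---|---|---|---|---|---|---|
| 3 | 3 | 1.19 | 1.19 | 0.01% | 15.9% | 1.5% |
| 4 | 3 | 1.28 | 0.97 | 0.08% | 32.5% | 1.6% |
| 3 | 6 | 1.09 | 2.18 | 0.00% | 99.97% | 99.7% |
| 4 | 6 | 1.12 | 1.68 | 0.00% | 99.99% | 99.7% |

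A separate run of 200,000 trials gave 16.2% and 31.8% for the summed rates at 3 per month. With uneven sites (an assumed 2.0, 0.7 and 0.3 per month) the sum passed in 25% of trials and the crude average in 0.7%. About 13% of those trials had a site with fewer than two patients. The slowest site accounts for most of this: its mean count is 0.3 × 12 = 3.6, and P(n < 2) = e^(−3.6) × (1 + 3.6) = 12.6%.

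**4. Could the bias lift the crude average to 4.17?** With 50 patients, each site's span would have to shrink to 16.67/4.17 = 4 months (3 sites) or 12.5/4.17 = 3 months (4 sites) out of 12.

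**The case against.** A reader might infer that the SAP's rule makes the recruitment target too easy to meet. The documents do not support that. The only overall figure in 7.1.1 is the crude average of site rates, while 4.17 is an all-site total, so the average is lower by a factor of 3 or 4. This outweighs the denominator bias. Even at the expected 6 per month the average is about 2.2 or 1.7 and almost never passes, against the stated 99.7%. The 16% and 32% arise only if the site rates are summed, which the SAP does not do. It would be equally wrong to say that all idle months are left out, since only the two ends are lost.

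It can also be said that the outcome is descriptive, that this is a pilot, and that the bias is modest at the accrual the sponsor expected (9% to 12%). That is fair, and it limits the severity. It does not remove the point. The site rates are reported in their own right and are inflated however they are combined. An opposing error in the averaging does not make the denominator right: if only the averaging were repaired, by summing, the excess chance of passing at 3 per month would become real.

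**Conclusion.** The concern stands in a limited form, as a change that should be made. Each site's recruitment rate is biased upward by construction, most at small sites, is undefined at a site with one patient, and is not on the calendar basis of its target. Under equal sites open 12 months with Poisson accrual, the median overstatement is 19% to 28% at a true total of 3 per month and 9% to 12% at 6 per month. Late starts or final stalls would make it larger. The size in this trial cannot be known from the SAP, which gives no opening or closing dates. As written, pass or fail is governed by the mismatch between a site average and an all-site total, so the denominator does not by itself create a lenient verdict.

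**What to change.** In 7.1.1, outcome 1:

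- Define each site's denominator as (date enrolment closed at the site − date the site was activated, or restarted for the multi-centre phase at KGH) / 30.4. This also gives a rate for a site with one patient.
- For the verdict against 4.17, replace the crude average by an all-site rate on the same calendar basis: total randomized over the multi-centre enrolment period, or the sum of the open-time site rates. Name one of the two. They differ if sites opened at different times, and the first is closer to the count in Appendix B.
- Keep the first-to-last rate, if wanted, as a descriptive line without a target.

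Both changes must be made together. Correcting the denominator alone would lower a figure that is already on the wrong scale for its target. The cost is SAP wording and two dates per site, which the coordinating unit should hold. The reported site rates become somewhat less favourable. Section 4.2 indicates that enrolment is already complete, so the reason for the change should be recorded as agreement with Appendix B.

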7.1.2 Secondary Outcomes

- 1) Coronary artery calcification progression:
 - a) the percent and absolute change of the Agatston and volume calcium scores (CT scan) will be assessed at study exit vs. baseline. Included measures will be: Total CAC, Left Main CAC, Right Coronary Artery CAC, Left Anterior Descending CAC, Circumflex CAC, and Posterior Descending Artery CAC.
 - b) the proportion of participants with a 15% or greater increase in Agatston and volume calcium scores will be assessed at study exit vs baseline.
- 2) Coronary artery calcification regression: the proportion of participants with a 10% or greater decrease in Agatston and volume calcium scores will be assessed at study exit vs baseline.
- 3) Aortic valve calcification progression: the absolute and percentage change of the Agatston and volume calcium scores (CT scan) will be assessed at study exit vs. baseline.
- 4) Mitral valve calcification progression: the absolute and percentage change of the Agatston and volume calcium scores (CT scan) will be assessed at study exit vs. baseline.
- 5) AAC score: the AAC score (mean score in L1-L4, mean number of positive segments, mean total severity using lateral lumbar spine radiographs) will be assessed at study exit vs. baseline.
- 6) Biomarkers of vitamin K status: Gas6, PK, MK4, osteocalcin Gla, osteocalcin Glu, osteocalcin Gla to Glu ratio, percent of osteocalcin undercarboxylated, and dpucMGP will be assessed at baseline, four, eight and study exit. PIVKA-II will be assessed at baseline and study exit.
- 7) Thoracic vertebral fractures: The prevalence and incidence of thoracic vertebral fractures (anterior and lateral radiographs) will be assessed at baseline and study exit.
- 8) Lumbar vertebral fractures: The prevalence and incidence of lumbar vertebral fractures (anterior and lateral radiographs) will be assessed at baseline and study exit.
- 9) Events of clinical interest:

The presence or absence and total of the following events will be assessed across the study duration per patient:

 - i) Hospitalizations
 - ii) Cardiovascular events: acute coronary syndrome, congestive heart failure, stroke, transient ischemic attack, amputation, and cardiac (symptom-driven) (cerebral or peripheral) revascularization procedure, or cardiac arrest
 - iii) Thrombosis: deep vein thrombosis and pulmonary embolism
 - iv) HD access thrombosis. Fistula and/or graft thrombosis or dialysis catheter thrombosis
 - v) Mortality: all-cause and cardiovascular cause

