1.3 Purpose, Usage and Target Audience of This Document

This document provides a detailed description of the analysis plan for the iPACK-HD trial. This document is meant to be used in conjunction with the study protocol. This document does not subsume the protocol, but several elements of the protocol, such as the sample size justification, are reproduced herein for completeness. This document has the following purposes:

1. Provides a written agreement between the Principal Investigator, lead study statistician and data analysts regarding exactly what analysis will be performed.
2. Provides a record of the analysis plan specified prior to unblinding treatment assignments that may be included as supplementary study documentation with the primary study publication.
3. Provides clear specifications for the analyst(s) performing the data filtering/transformation, variable derivations, statistical analyses, and report generation.

This document follows the guidance published in JAMA by Gamble et al (2017) and referenced at <https://www.equator-network.org/reporting-guidelines/guidelines-for-the-content-of-statistical-analysis-plans-in-clinical-trials/>.¹ The SAP checklist is completed in Appendix A.

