7.2 Analysis Methods

The feasibility outcomes will be presented descriptively overall as rates or proportions. In addition, compliance with study medication, dropout rate, and adherence to study protocol will be compared by arm. Reasons for loss-to-follow-up and non-compliance will be tabulated.

For the binary outcomes, we will provide counts and percentages by arm and compare arms by the Mantel-Haenszel test stratified by site and diabetes (or Fisher's Exact Test for outcomes with less than 20 events or non-events).

This study has many continuous outcomes that are far from normally distributed. For all continuous outcomes, we will report medians and quartiles by arm and compare arms by the Van Elteren test stratified by site and diabetes. Selected continuous variables may be depicted by clustered boxplots comparing the two arms over time. Biomarkers assessed at multiple time points will have both absolute value and change from baseline compared by arm at each time point.

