7.3 Missing Data

The number of missing items will be presented by arm for each outcome. Imputation will not be performed for this feasibility/phase II pilot study.

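### Does percent change at single coronary vessels and valves need a stated rule for a zero baseline score?

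*SAP*

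**What the plan says.** Item 1a of SAP section 7.1.2 states that "the percent and absolute change of the Agatston and volume calcium scores (CT scan) will be assessed at study exit vs. baseline". It then lists the coronary measures: "Included measures will be: Total CAC, Left Main CAC, Right Coronary Artery CAC, Left Anterior Descending CAC, Circumflex CAC, and Posterior Descending Artery CAC". Items 3 and 4 plan the same for the valves: "Aortic valve calcification progression: the absolute and percentage change of the Agatston and volume calcium scores" and "Mitral valve calcification progression: the absolute and percentage change of the Agatston and volume calcium scores".

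For analysis, section 7.2 says: "For all continuous outcomes, we will report medians and quartiles by arm". Arms are compared by the Van Elteren test stratified by site and diabetes. On missing values, section 7.3 says: "The number of missing items will be presented by arm for each outcome", and it rules out imputation. Section 5.2 analyses whatever data are available.

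The only calcium threshold is the entry rule in sections 4.1 and 4.2, a patient-level CAC score of at least 30 AU. No section says how percent change is derived when a vessel or valve scores zero at baseline.

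**The concern.** A patient can pass the entry threshold on calcium in one or two vessels and have none in another vessel or on a valve. Percent change there has a zero denominator, whether the exit score is zero or positive. One analyst might leave such patients out, and another might record zero-to-zero as 0% change. The medians and quartiles would differ, so a published figure could rest on a choice made after the data were seen.

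The SAP also sets itself a standard on this. Section 1.3 says the document "Provides clear specifications for the analyst(s) performing the data filtering/transformation, variable derivations, statistical analyses, and report generation". A zero-denominator rule is a variable derivation, so it cannot simply be left to the protocol. The SAP is this detailed elsewhere: section 7.1.1 fixes a month at 30.4 days.

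**Working it through.** **Comparisons exposed.** Five single vessels × 2 scores = 10, and two valves × 2 scores = 4, giving 14. Adding total CAC × 2 scores gives 16 percent-change comparisons of calcium scores. The entry threshold protects the 2 for total CAC. The 16 matching absolute-change comparisons are always defined when both scans are read.

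**Patients affected.** The SAP does not give the share z with a zero baseline at a vessel or valve, and it may be nil at some. Assumed shares of 10%, 20% and 30% of the planned 80 (section 4.3) give 8, 16 and 24 patients. These are ceilings, because percent change also needs an exit scan. Section 7.1.1 tolerates dropout of just under 20%, with deaths not counted as dropout.

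**Effect on a reported median.** Compare two readings.

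- Zero-baseline patients left out: the median is the 50th percentile of patients with baseline calcium at that vessel or valve.
- All zero-baseline patients stay at zero and are coded 0%, and everyone else progresses: the overall median is the (0.5 − z)/(1 − z) quantile of those same patients.

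| Assumed z | Formula | Percentile |
|---|---|---|
| 10% | 0.40/0.90 | 44th |
| 20% | 0.30/0.80 | 38th |
| 30% | 0.20/0.70 | 29th |

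The result holds for any distribution of the positive changes. It is the largest shift between these two readings: patients who go from zero to positive stay undefined under both and so shrink it.

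**Which reading the plan leads to.** Both scores exist, but their ratio does not. Recording a percentage for it means supplying a value. Under section 7.3 nothing is imputed, and software returns missing on division by zero. Carried out as written, the plan computes percent change only where baseline is above zero.

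**Whether that reading harms the comparison.** It selects patients on a baseline value, so it narrows the population without biasing one arm against the other. It also reduces the number analysed. The SAP's own figure in section 4.3 is 80% power for the Wilcoxon test at concordance 0.68 with 40 per arm. The formula Φ(√(12·N·0.25)·(0.68 − 0.5) − 1.96) with N = 80 gives 79.6%, so the figure is reproduced. With N = 72, 64 and 56 it gives 75.3%, 70.3% and 64.5%. Stating the rule would leave these numbers as they are, because the same patients would be left out.

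**Whether undefined ratios can be told from absent scans.** Section 7.3 counts missing items by arm for each outcome. Taking absolute and percent change as separate outcomes, suppose an arm has m patients without a usable pair of scans and k with a zero baseline and both scans. Absolute change then shows m missing and percent change shows m + k, so the difference is k. Section 6.4 also describes baseline calcium scores by arm.

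**The case for a change.** The strongest contrary argument is that section 7.3 is about missing data, and these data are not missing. Both scans were read, and calling zero-to-zero no change arguably imputes nothing. On that view the SAP does not choose between the readings, and leaving the ratio missing drops patients who newly calcify.

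An illustrative simulation supports the view that the choice can matter. It assumed 30% zero baselines, 40 per arm and an unstratified rank-sum test, and compared four rules. The p < 0.05 verdict differed between rules in about 8% of trials with no effect and 32% with an assumed effect. In the effect setting, power ran from 43% to 65%. One possible mixture, coding zero-to-zero as 0% while leaving zero-to-positive missing, selects on the outcome and could bias a comparison.

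Part of this stands. The SAP is silent on the point, and the no-imputation reading is strong but not explicit. The simulation, however, rests on assumed settings and shows direction only. Each of the four rules kept the false-positive rate between 4.4% and 4.9%. The rules other than leaving zeros out all supply a value, or use an offset, that the SAP does not mention. Patients who newly calcify are not lost to the trial, because absolute change is planned for the same vessels and valves and includes them. If the independent re-analysis in section 8.2 extends to single vessels, a difference between two analysts would come to light there.

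**Conclusion.** The SAP has a small gap that analysts fill sensibly, and no change is needed. Up to 14 exploratory percent-change comparisons lack a written zero-baseline rule. With no imputation and an undefined ratio left missing, the plan already does what such a rule would say: it calculates percent change where baseline is above zero. Writing that down would change no analysis, and no between-arm bias arises from it.

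Little depends on these figures. The primary outcomes are feasibility measures (section 7.1.1), and arm comparisons are exploratory (section 4.4). Section 8.2 names CAC progression by percent change as the main secondary outcome, and for total CAC the entry threshold protects it. Absolute change covers every affected vessel and valve.

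The conclusion rests on two readings: that ruling out imputation leaves an undefined ratio missing, and that section 7.3 counts absolute and percent change separately. The zero share is unknown. The shift to the 44th, 38th or 29th percentile applies only if an analyst codes unchanged zeros as 0%, and then only at most.
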